# 10.3. Efficacy assessment

Magnetic contrast enhanced brain resonance imaging (MRI) and body CT scan will be performed at baseline and every 8 weeks up to 12 months and according to normal practise thereafter. All lesions selected as target and non-target lesions in the initial evaluation will be measured according to the aforementioned timeline, until disease progression. Imaging tests will be performed using the same method each time.

After local treatment, intracranial lesions (both target and non-target lesions) will be considered as non-evaluable (NE), brain MRI be performed as per protocol (every 8 weeks until first year and according to normal practise thereafter) however disease will be followed only to determine iPFS (unequivocal disease progression or new lesions).

#### 10.3.1 Assessment of response guidelines

Table 12. Criteria for disease evaluation for target lesions

CR	Disappearance of all target lesions. Any pathological lymph nodes (whether target or non-target) must have reduction in short axis to <10 mm
PR	At least a 30% decrease in the sum of diameters of target lesions, taking as reference the baseline sum diameters.
PD	At least a 20% increase in the sum of diameters of target lesions, taking as reference the smallest sum on study (this includes the baseline sum if that is the smallest on study). In addition to the relative increase of 20%, the sum must also demonstrate an absolute increase of at least 5 mm. (Note: the appearance of one or more new lesions is also considered progression).
SD	Neither sufficient shrinkage to qualify for PR nor sufficient increase to qualify for PD, taking as reference the smallest sum diameters while on study.

# Table 13. Criteria for disease evaluation for non-target lesions

CR	Disappearance of all non-target lesions and normalisation of tumour marker level. All lymph nodes must be non-pathological in size (<10 mm short axis).
Non-CR/non-PD	Persistence of one or more non-target lesion(s) and/or maintenance of tumour marker level above the normal limits.
PD	Unequivocal progression (see comments below) of existing non-target lesions. (Note: the appearance of one or more new lesions is also considered progression).

# **Table 14: Overall Response Assessment (RECIST)**

Target Lesions	Non-target Lesions	New Lesions	Overall Response	
CR	CR	No	CR	
CR	Non-CR/non-PD	No	PR	

CR	Not evaluated	No	PR
PR	Non-PD or not all evaluated	No	PR
SD	Non-PD or not all evaluated	No	SD
Not all evaluated	Non-PD	No	NE
PD	PD Any		PD
Any	PD	Yes or No	PD
Any Any		Yes	PD

CR = complete response, PR = partial response, SD = stable disease, PD = progressive disease, and NE = not evaluable

Disease progression and response evaluations for intracranial and extracranial disease will be determined according to the definitions established in the Response Evaluation Criteria in Solid Tumours (RECIST 1. 1); Minor modifications will be applied to the assessment of intracranial lesions:

Intracranial response assessment: The Investigator modified RECIST 1.1 criteria will be used to evaluate the intracranial response. The modifications to RECIST 1.1 impact the number and the minimal size of the target lesions selected at baseline. Up to 5 intracranial lesions should be selected as target; based on size and evaluation/tracking feasibility. All the remaining brain lesions different from these 5 target lesions must be considered as non-target lesions (independently of their size). The size of target and non-target lesions must be measured. Measurable lesions are defined as those that can be accurately measured in at least one dimension with the longest diameter  $\geq 5$  mm when evaluated by contrast-enhanced MRI.

For intracranial response, target lesions as small as 5 mm may be selected, however the scanning should be in accordance with modified RECIST 1.1 (contiguous slices of maximum thickness corresponding to half the size of the lesion.

Contrast-enhanced MRI is the only modality accepted for the assessment of intracranial lesions. For justified exceptions please, contact with the sponsor:

10.3.2 Measurable and non-measurable definitions for response assessment

- RECIST 1.1 standard definitions will be used
  - 10.3.3 Measurable and non-measurable definitions for intracranial response assessment
- Measurable intracranial lesion: a measure that can be accurately measured at least in one dimension with the longest diameter ≥ 5 mm when evaluated by contrast-enhanced MRI.
- Non-measurable intracranial lesion: all other lesions, including those too small to be considered measurable (longest diameter < 5 mm).

- Measurable intracranial disease: The presence of at least one measurable lesion.
- Non-measurable intracranial (only) disease: The presence of only non-measurable lesions, which at baseline excludes the patient for participation in the study.

#### 10.4. Safety assessment

All patients included in the trial and have received at least one dose of study medication will be evaluable for safety analysis.

Safety and tolerability of study medication will be determined by evaluating the type, incidence, frequency, severity and relation to the treatment of reported adverse events, physical examinations and laboratory tests. Any signs and/or symptoms associated with the existing tumour at baseline worsening (in severity or frequency) during the trial should be reported as an adverse event. They should record all adverse events according to the NCI-CTCAE version 4.03 in each study visit.

#### 10.5. Definition of study populations

Data of study will be analysed in the following populations:

- 1. ITT: All patients that have been enrolled in the trial.
- 2. Evaluable population per protocol (PP): All patients fulfilling all eligibility criteria and having at least two valid tumour assessments (baseline and one evaluation MRI or CT-scan) without any protocol deviation that makes the patient invalid for the primary endpoint evaluation.
- 3. Safety population: All patients receiving at least one dose of treatment.

#### 10.6. Statistical analysis

For each categorical variable, the results will be summarized by frequencies and percentages. For each continuous variable, the results will be summarized by descriptive statistics such as median, range, and interquartile range or by means, standard deviations and 95% confidence intervals (CIs). For proportions, point estimates and exact 95% confidence intervals will be calculated. For time to event endpoints, Kaplan-Meier estimates at selected time points and corresponding curves will be presented. Time to event is derived relative to the first study treatment administration. Laboratory values will be expressed as the absolute values and as grading (ordinal categorical variables) according to NCI CTCAE v 4.03.

Treatment-emergent AE (AEs starting after the administration of study treatment and up to study completion) will be summarized by system organ class and preferred term. Grading will be presented by type and grade in tables showing frequency and percentage of the within-patient worst grades. In addition, grade ≥3 AEs will be summarized separately. Full analysis details will be outlined in the statistical analysis plan (SAP).

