- 14. Medical, psychiatric, cognitive or other conditions that may compromise the patient's ability to understand the patient information, give informed consent, comply with the study protocol or complete the study.
- 15. Known hypersensitivity to encorafenib, binimetinib or their components.
- 16. Persisting toxicity related to prior therapy of Grade >1 NCI-CTCAE v 4.03; however, alopecia and sensory neuropathy Grade ≤ 2 is acceptable.
- 17. Female patients who are pregnant or breastfeeding or male or female patients of reproductive potential who are not willing to employ highly effective birth control from screening to 180 days after the last dose of study treatment.
- 18. Known alcohol or drug abuse.
- 19. Inability to swallow tablets or capsules.
- 20. Total lactase deficiency or glucose-galactose malabsorption.

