#### 9.2.1.1. Adverse Event (AE)

An AE is defined as any untoward medical occurrence in a patient or clinical investigation subject administered a pharmaceutical product and which does not necessarily have to have a causal relationship with this treatment. An adverse event (AE) can therefore be any unfavourable and unintended sign (including an abnormal laboratory finding, for example), symptom, or disease temporally associated with the use of a medicinal product, whether considered related to the medicinal product.

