# 9.4. Reporting

# 9.4.1. Reporting an Adverse Event

Adverse events (serious and non-serious) spontaneously reported by the patient and/or in response to an open question from the study personnel or revealed by observation will be recorded during the study at the investigational site. Information about AEs (including SAEs) will be collected from the signing of Informed Consent at least until the end of treatment visit or up to resolution. For each AE, the investigator will evaluate and report the onset (date and time), resolution (date and time), severity, causality, action taken, outcome, and whether it caused the patient to discontinue the study.

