#### 10.7. Statistical Methods

Analysis will be based on observed data, and missing data for dropouts are not replaced by methods like LOCF (last option carried forward).

Continuous data will be presented with the number of observations, mean value + standard deviation, median value + minimum and maximum. Categorical data will be presented as counts and percentages. Individual subject data will be listed.

Individual and summary vital signs, ECG parameters, clinical laboratory data (haematology, serum biochemistry and urinalysis) will be presented in tabular form. For the values outside the reference range will be flagged and for the clinically significantly abnormal values will be listed in tabular form. Adverse events will be tabulated by system organ class and preferred term after medical coding using the NCI CTCAE v 4.03.

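### The treatment-emergent definition in protocol section 10.6 counts new onset only, so a pre-dose adverse event that worsens on treatment is missed, and SAP section 5 applies no emergence rule at all

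*Combined protocol and SAP*

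**What the plan says.** - **Counting rule.** Protocol section 10.6 summarises events by system organ class and preferred term using this definition: "Treatment-emergent AE (AEs starting after the administration of study treatment and up to study completion". It tests onset only. The same paragraph promises within-patient worst grades and adds: "In addition, grade ≥3 AEs will be summarized separately".
- **Collection window.** Protocol section 9.4.1: "Information about AEs (including SAEs) will be collected from the signing of Informed Consent". Screening may run for 28 days before day 1, so an AE can have a start date before the first dose.
- **Worsening.** Protocol section 10.4 covers it for one class only: signs or symptoms "associated with the existing tumour at baseline worsening (in severity or frequency) during the trial should be reported as an adverse event".
- **AE definition.** Section 9.2.1.1 includes "any unfavourable and unintended sign (including an abnormal laboratory finding, for example), symptom, or disease temporally associated with the use of a medicinal product". It does not mention worsening of an existing condition. Section 9.1.1 places active conditions at entry in the medical history.
- **Who may enter.** Exclusion criterion 16 bars "Persisting toxicity related to prior therapy of Grade >1 NCI-CTCAE v 4.03", but accepts alopecia and sensory neuropathy up to grade 2. Inclusion criterion 8 allows AST and ALT up to 5 x ULN with liver metastases. Cohort 2 enters with symptoms from brain metastases.
- **Laboratory data.** Section 10.6: "Laboratory values will be expressed as the absolute values and as grading (ordinal categorical variables) according to NCI CTCAE v 4.03". Section 10.7: "clinical laboratory data (haematology, serum biochemistry and urinalysis) will be presented in tabular form", with out-of-range values flagged.
- **SAP.** Section 5 (Tables 124-130) counts or lists AEs, toxicities, grade 3 or higher events and SAEs in the safety population. It does not use the term treatment-emergent, a baseline grade or an onset filter.

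**The concern.** Toxicity before and after local treatment is a secondary objective in both cohorts. The study is single-arm, so the absolute incidence is itself the result and no control arm would share a counting error.

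An onset-only rule asks when an event began and ignores what happened to it on drug. A patient whose grade 2 neuropathy was logged as an AE during screening and who reaches grade 3 on treatment has a pre-dose start date, so the rule excludes the event. Such conditions are admitted by design. For transaminases, the eligibility ceiling with liver metastases (5 x ULN) is also where the enzyme threshold of the Grade 3 liver entry in Table 10 begins. The SAP, to which section 10.6 defers for full details, neither repeats the rule nor replaces it.

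**Working it through.** The plan gives no figure to reproduce, because the question is one of definition. The check sorts events by when and how they were recorded and applies each rule as written.

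| Event | Protocol 10.6 treatment-emergent table | SAP section 5 | Rule with a worsening clause |
|---|---|---|---|
| A. Starts after first dose | counted | counted | counted |
| B. AE recorded between consent and first dose, grade unchanged | not counted | counted | not counted |
| C. AE recorded between consent and first dose, grade rises on treatment | **not counted** | counted | counted, at post-dose worst grade |
| D. Non-tumour condition held only in medical history, worsens | counted only if a new AE is opened | counted only if a new AE is opened | counted, if 10.4 is extended |
| E. Tumour-associated sign or symptom, worsens (10.4 applies) | depends on the start date given | counted | counted |

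**Row C** is the defect in the protocol rule. No other section adds a worsening clause, and the column headings of SAP Tables 130 and 168 show one grade and one start date per event, with no grade-change date.

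**Row B** is the defect in the SAP. With no emergence rule, an AE that began before dosing and never changed counts as an on-study AE.

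**Row D** is a recording gap ahead of both rules. No section requires worsening of a non-tumour baseline condition to be entered as a new AE.

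**Row E** is unresolved because 10.4 does not say whether the worsening takes its own start date.

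**Laboratory abnormalities** have a second route. Protocol sections 10.6 and 10.7 grade and tabulate laboratory values without an onset restriction, so a transaminase rise on treatment should appear there whatever its AE start date. The SAP contains no laboratory grade table or baseline-to-worst shift table to carry this out. The route also cannot capture a symptom such as neuropathy.

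**Direction.** Against the protocol's treatment-emergent table, a worsening clause can only add events (row C, and possibly E), so within that table the omission lowers the count. Against the SAP tables the change can go either way: row B events drop out, row D events may come in, and some grades may rise.

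**Weight of one patient.** Planned numbers are 48 + 15 = 63. Taking all planned patients as dosed:

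- overall: 1/63 = 1.6 percentage points
- cohort 1: 1/48 = 2.1 percentage points
- cohort 2: 1/15 = 6.7 percentage points

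The documents do not say how many patients enter with such a condition, how many have it logged as a pre-dose AE, or how many worsen. The total effect cannot be computed.

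**The case against.** A reader might infer that on-treatment worsening is left out of the safety summaries altogether and that reported toxicity is biased downwards. The documents do not support that, for these reasons.

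- The laboratory summaries in 10.6 and 10.7 have no onset filter, and the toxicity endpoints in 10.2 include changes in laboratory values, vital signs, ECG and LVEF. A liver-enzyme example on its own therefore does not show a lost signal.
- The sentence on grade 3 or higher events in 10.6 says only AEs. Whether the onset rule governs it is unclear.
- The SAP tables apply no onset filter, so any worsening that is recorded as an AE is counted there.
- Tumour-associated worsening must be reported under 10.4, which largely covers the neurological symptoms of cohort 2. SAP section 6.2 also compares those symptoms at baseline and two assessments.
- Entry conditions go to medical history. If a baseline abnormality was never logged as a pre-dose AE, its worsening could be entered as a new AE starting after dosing, which would meet the rule.

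All of this stands and narrows the point. It does not remove it. Collection from consent makes a pre-dose AE possible, 10.6 then excludes it whatever it becomes, and nothing guarantees that a worsened non-tumour condition receives a new record. That the SAP applies no filter is a second inconsistency, because it mixes unchanged pre-dose events with those that emerged on treatment.

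**Conclusion.** The point holds in a limited form. The protocol's treatment-emergent table misses AEs recorded between consent and first dose that worsen on treatment. SAP section 5 has no emergence rule and so also counts pre-dose AEs that did not worsen. Neither output isolates what began or worsened on treatment, and 10.4 covers worsening only for tumour-associated signs and symptoms.

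The size is unknown. One patient is worth 1.6 points overall, 2.1 in cohort 1 and 6.7 in cohort 2; these are weights, not estimates. The cohort 2 figure needs most care, since much of that cohort's baseline symptomatology falls under 10.4. The conclusion assumes that 10.6 is applied as written and that a worsened AE keeps its original start date, which the documents neither state nor exclude. It does not extend to a claim that overall toxicity reporting is biased downwards.

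**What to change.** 1. In protocol section 10.6, define treatment-emergent AEs as those that start, or worsen in CTCAE grade relative to before the first dose, after the first administration of study treatment. Count the post-dose worst grade.
2. Use the same definition in SAP Tables 124-129, and state whether the separate grade 3 or higher summary follows it.
3. Extend protocol section 10.4 so that worsening of any baseline condition, not only tumour-associated signs and symptoms, is recorded as an AE with its own start or grade-change date.
4. Add a laboratory table of baseline against worst post-dose grade to the SAP, so that the grading promised in 10.6 is delivered.

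The cost is one sentence each in 10.6, 10.4 and SAP section 5, plus one table. AEs are already graded at each visit; records of events that began before dosing would need checking for a grade-change date. Rates may move in either direction relative to the unfiltered SAP tables, because worsened events are captured and unchanged pre-dose AEs drop out.

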#### 10.7. Statistical Methods

Analysis will be based on observed data, and missing data for dropouts are not replaced by methods like LOCF (last option carried forward).

Continuous data will be presented with the number of observations, mean value + standard deviation, median value + minimum and maximum. Categorical data will be presented as counts and percentages. Individual subject data will be listed.

Individual and summary vital signs, ECG parameters, clinical laboratory data (haematology, serum biochemistry and urinalysis) will be presented in tabular form. For the values outside the reference range will be flagged and for the clinically significantly abnormal values will be listed in tabular form. Adverse events will be tabulated by system organ class and preferred term after medical coding using the NCI CTCAE v 4.03.

#### 11. DIRECT ACCESS TO SOURCE DATA/DOCUMENTS

#### 11.1. Source data definition

Source data is defined as all data in original records and certified copies of original records of clinical findings, observations, or other activities in a clinical trial that are necessary for the reconstruction and evaluation of the trial.

The Investigator must keep a file (medical file, original medical records) on paper or electronically for every subject in the trial. It must be possible to identify each subject by using this subject file. This file will contain the demographic and medical information for the subject listed below and should be as complete as possible.

- Subject's full name, date of birth, sex, height, weight
- Medical history and concomitant diseases
- Prior and concomitant therapies (including changes during the trial)
- Trial identification, that is, the Sponsor trial number for this clinical trial, and subject number
- Dates for entry into the trial (informed consent) and visits to the site
- Any medical examinations and clinical findings predefined in this clinical trial protocol
- All AEs
- Date that the subject left the trial including any reason for early withdrawal from the trial or IMP (if applicable).

All documents containing source data must be filed, including, but not limited to CT or MRI scan images, ECG recordings, and laboratory results. Such documents must bear the subject number and the date of the procedure. If possible, this information should be printed by the instrument used to perform the assessment or measurement. Medical evaluation of such records will be performed as necessary; all evaluations will be documented, signed, and dated by the Investigator.

Electronic subject files will be printed whenever the Monitor performs source data verification. Printouts will be signed and dated by the Investigator, countersigned by the Monitor, and will be secured in a safe place at the site.

#### 11.2. Study Monitoring

During the study, according to monitoring plan, a monitor from regular contact with the investigational site, for the following:

- Provide information and support to the investigator(s)
- Confirm that facilities remain acceptable
- Confirm that the investigational team is adhering to the protocol, data are being accurately recorded in the case report forms, and that investigational product accountability checks are being performed
- Perform source data verification. This includes a comparison of the data in the case report forms with the patient's medical records at the hospital or practice, and other records relevant to the study. This will require direct access to all original records for each patient (e.g. clinic charts).
- Record and report any protocol deviations not previously sent to

 Confirm that AEs and SAEs have been properly documented on CRFs and confirm that all SAEs have been forwarded to MFAR, additionally, confirm that all the SAEs that met criteria for reporting have been forwarded to the IRB

The monitor will be available between visits if the investigator(s) or other staff members need information or advice.

#### 11.3. Audits and Inspections

Authorized representatives of Sponsor, a regulatory authority, an Independent Ethics Committee or an Institutional Review Board may visit the site to perform audits or inspections, including source data verification. The purpose of a Sponsor audit or inspection is to systematically and independently examine all study-related activities and documents to determine whether these activities were conducted, and data were recorded, analysed, and accurately reported according to the protocol, Good Clinical Practice guidelines of the International Conference on Harmonization, and any applicable regulatory requirements. The investigator should contact Sponsor through immediately if contacted by a regulatory agency about an inspection.

